7.3.1.3. Serious Adverse Event Paper Reporting Process

- All SAEs will be recorded on the SAE report form and submitted by faxing or emailing the report form within 24 hours of the investigator's knowledge of the event to the attention of Gilead DSPH or to the designated CRO.

Gilead DSPH:

Fax: PPD

Email: PPD

7.3.1.4. Electronic Serious Adverse Event (eSAE) Reporting Process

- Site personnel record all SAE data in the eCRF database and from there transmit the SAE information to Gilead DSPH within 24 hours of the investigator's knowledge of the event. Detailed instructions can be found in the eCRF completion guidelines.
- If for any reason it is not possible to record the SAE information electronically, ie, the eCRF database is not functioning, record the SAE on the paper SAE reporting form and submit within 24 hours to: Email: PPD and Fax: PPD
- As soon as it is possible to do so, any SAE reported via paper must be transcribed into the eCRF Database according to instructions in the eCRF completion guidelines.
- If an SAE has been reported via a paper form because the eCRF database has been locked, no further action is necessary.

- For fatal or life-threatening events, copies of hospital case reports, autopsy reports, and other documents are also to be submitted by e-mail or fax when requested and applicable. Transmission of such documents should occur without personal subject identification, maintaining the traceability of a document to the subject identifiers.
- Additional information may be requested to ensure the timely completion of accurate safety reports.
- Any medications necessary for treatment of the SAE must be recorded onto the concomitant medication section of the subject's CRF/eCRF and the event description section of the SAE form.

7.4. Gilead Reporting Requirements

Depending on relevant local legislation or regulations, including the applicable US FDA Code of Federal Regulations, the EU Clinical Trials Directive (2001/20/EC) and relevant updates, and other country-specific legislation or regulations, Gilead may be required to expedite to worldwide regulatory agencies reports of SAEs, serious adverse drug reactions (SADRs), or suspected unexpected serious adverse reactions (SUSARs). In accordance with the EU Clinical Trials Directive (2001/20/EC), Gilead or a specified designee will notify worldwide regulatory agencies and the relevant IEC in concerned Member States of applicable SUSARs as outlined in current regulations.

Assessment of expectedness for SAEs will be determined by Gilead using reference safety information specified in the IB or relevant local label as applicable.

All investigators will receive a safety letter notifying them of relevant SUSAR reports associated with any study drug. The investigator should notify the IRB or IEC of SUSAR reports as soon as is practical, where this is required by local regulatory agencies, and in accordance with the local institutional policy.

7.5. Clinical Laboratory Abnormalities and Other Abnormal Assessments as Adverse Events or Serious Adverse Events

Laboratory abnormalities are usually not recorded as AEs or SAEs. However, laboratory abnormalities (eg, clinical chemistry, hematology, and urinalysis) that require medical or surgical intervention or lead to investigational medicinal product interruption or discontinuation must be recorded as an AE, as well as an SAE, if applicable. In addition, laboratory or other abnormal assessments (eg, electrocardiogram, X-rays, vital signs) that are associated with signs and/or symptoms must be recorded as an AE or SAE if they meet the definition of an AE or SAE as described in Sections 7.1.1 and 7.1.2 respectively. If the laboratory abnormality is part of a syndrome, record the syndrome or diagnosis (ie, anemia) not the laboratory result (ie, decreased hemoglobin).

Severity should be recorded and graded according to the GSI Grading Scale for Severity of Adverse Events and Laboratory Abnormalities ([Appendix 4](#)).

For AEs associated with laboratory abnormalities, the event should be graded on the basis of the clinical severity in the context of the underlying conditions; this may or may not be in agreement with the grading of the laboratory abnormality.

7.6. Toxicity Management

Treatment-emergent toxicities will be noted by the investigator and brought to the attention of the Gilead Sciences Medical Monitor or designee. Whether or not considered treatment-related, all subjects experiencing AEs must be monitored periodically until symptoms subside, any abnormal laboratory values have resolved or returned to baseline levels or they are considered irreversible, or until there is a satisfactory explanation for the changes observed.

Clinical events and clinically significant laboratory abnormalities will be graded according to the GSI Grading Scale for Severity of Adverse Events and Laboratory Abnormalities ([Appendix 4](#)). Grade 3 and 4 clinically significant laboratory abnormalities should be confirmed by repeat testing as soon as practical to do so, and preferably within 3 calendar days after receipt of the original test results. If Grade 4 lab abnormalities are confirmed for either subjects with normal hepatic function (healthy controls) or subjects with impaired hepatic function, study drug will be discontinued permanently. However, these subjects will be followed for resolution as per [Section 6.6](#).

Any questions regarding toxicity management should be directed to the Gilead Medical Monitor.

7.7. Special Situations Reports

7.7.1. Definitions of Special Situations

Special situation reports include all reports of medication error, abuse, misuse, overdose, reports of AEs associated with product complaints, and pregnancy reports regardless of an associated AE.

Medication error is any unintentional error in the prescribing, dispensing, or administration of a medicinal product while in the control of the health care provider, subject, or consumer.

Abuse is defined as persistent or sporadic intentional excessive use of a medicinal product by a subject.

Misuse is defined as any intentional and inappropriate use of a medicinal product that is not in accordance with the protocol instructions or the local prescribing information.

An overdose is defined as an accidental or intentional administration of a quantity of a medicinal product given per administration or cumulatively which is above the maximum recommended dose as per protocol or in the product labelling (as it applies to the daily dose of the subject in question). In cases of a discrepancy in drug accountability, overdose will be established only when it is clear that the subject has taken the excess dose(s). Overdose cannot be established when the subject cannot account for the discrepancy except in cases in which the investigator has reason to suspect that the subject has taken the additional dose(s).

Product complaint is defined as complaints arising from potential deviations in the manufacture, packaging, or distribution of the medicinal product.

7.7.2. Instructions for Reporting Special Situations

7.7.2.1. Instructions for Reporting Pregnancies

The investigator should report pregnancies in female study subjects that are identified after initiation of study medication and throughout the study, including the post study drug follow-up period, to Gilead DSPH using the pregnancy report form within 24 hours of becoming aware of the pregnancy.

Refer to section 7.3 and the CRF/eCRF completion guidelines for full instructions on the mechanism of pregnancy reporting.

The pregnancy itself is not considered an AE nor is an induced elective abortion to terminate a pregnancy without medical reasons.

Any premature termination of pregnancy (eg, a spontaneous abortion, an induced therapeutic abortion due to complications or other medical reasons) must be reported within 24 hours as an SAE. The underlying medical reason for this procedure should be recorded as the AE term.

A spontaneous abortion is always considered to be an SAE and will be reported as described in Section 7.3. Furthermore, any SAE occurring as an adverse pregnancy outcome post study must be reported to Gilead DSPH.

The subject should receive appropriate monitoring and care until the conclusion of the pregnancy. The outcome should be reported to Gilead DSPH using the pregnancy outcome report form. If the end of the pregnancy occurs after the study has been completed, the outcome should be reported directly to Gilead DSPH. Gilead DSPH contact information is as follows:
Email: PPD and Fax: PPD

Pregnancies of female partners of male study subjects exposed to Gilead or other study drugs must also be reported and relevant information should be submitted to or Gilead DSPH using the pregnancy and pregnancy outcome forms within 24 hours. Monitoring of the subject should continue until the conclusion of the pregnancy. If the end of the pregnancy occurs after the study has been completed, the outcome should be reported directly to Gilead DSPH, fax number PPD or email PPD

Refer to [Appendix 3](#) for Pregnancy Precautions, Definition for Female of Childbearing Potential, and Contraceptive Requirements.

7.7.2.2. Reporting Other Special Situations

All other special situation reports must be reported on the special situations report form and forwarded to Gilead DSPH within 24 hours of the investigator becoming aware of the situation.

These reports must consist of situations that involve study drug and/or Gilead concomitant medications, but do not apply to non-Gilead concomitant medications.

Special situations involving non-Gilead concomitant medications does not need to be reported on the special situations report form; however, for special situations that result in AEs due to a non-Gilead concomitant medication, the AE should be reported on the AE form.

Any inappropriate use of concomitant medications prohibited by this protocol should not be reported as “misuse,” but may be more appropriately documented as a protocol deviation.

Refer to section 7.3 and the CRF/eCRF completion guidelines for full instructions on the mechanism of special situations reporting.

All clinical sequelae in relation to these special situation reports will be reported as AEs or SAEs at the same time using the AE CRF/eCRF and/or the SAE report form. Details of the symptoms and signs, clinical management, and outcome will be reported, when available.

8. STATISTICAL CONSIDERATIONS

8.1. Analysis Objectives and Endpoints

8.1.1. Analysis Objectives

The primary analysis objective of this study is to evaluate the PK of ENTO and/or its metabolites (if applicable) in subjects with impaired hepatic function (stratified by smoking status, as appropriate) relative to matched, healthy controls

The secondary objectives of this study are as follows:

- To evaluate the safety and tolerability of administration of ENTO in subjects with normal and impaired hepatic function
- To evaluate the potential impact of smoking on the PK of ENTO in subjects with moderate hepatic impairment

8.1.2. Primary Endpoint

The primary endpoints are the PK parameters AUC and C_{\max} of ENTO and/or its metabolites (if applicable).

8.1.3. Secondary Endpoint

The secondary endpoints are the incidences of adverse events and laboratory abnormalities.

8.2. Analysis Conventions

8.2.1. Analysis Sets

8.2.1.1. PK Analysis Set

The PK analysis set will include all enrolled/randomized subjects who received at least 1 dose of study drug (ENTO) and had at least 1 non-missing PK concentration data reported by PK lab for each respective analyte. This is the primary analysis set for PK summaries.

8.2.1.2. Safety Analysis Set

The safety analysis set will include all enrolled subjects who received at least 1 dose of study drug. This is the primary analysis set for safety summaries.

8.2.1.3. All Enrolled Analysis Set

The all enrolled analysis set will include all subjects who were enrolled into the study. This is the primary analysis set for safety listings.

8.3. Data Handling Conventions

For summary statistics, PK concentration values below the limit of quantitation (BLQ) will be treated as zero at predose and one-half of the lower limit of quantitation (LLOQ) for postdose timepoints, where LLOQ is corrected for the dilution factor (ie, reported dilution/dilution factor).

Laboratory data that are continuous in nature but are less than the lower limit of quantitation or above the upper limit of quantitation will be imputed to the value of the lower or upper limit minus or plus one significant digit, respectively (eg, if the result of a continuous laboratory test is < 20, a value of 19 will be assigned; if the result of a continuous laboratory test is < 20.0, a value of 19.9 will be assigned).

Missing data can have an impact upon the interpretation of the trial data. As this study is of short duration, it is anticipated that missing data will be minimal. In general, values for missing data will not be imputed. However, a missing pretreatment laboratory result would be treated as normal (ie., no toxicity grade) for the laboratory abnormality summary.

8.4. Demographic Data and Baseline Characteristics

Demographic and baseline measurements will be summarized and descriptive statistics will be provided.

8.5. Safety Analysis

All safety data collected on or after the date that study drug was first administered up to the date of last dose of study drug plus 30 days will be listed and summarized using safety analysis set.

8.5.1. Extent of Exposure

A subject's extent of exposure to study drug data will be generated from the study drug administration page in eCRF. Exposure data will be listed.

8.5.2. Adverse Events

Clinical and laboratory AEs will be coded using the Medical Dictionary for Regulatory Activities (MedDRA). System Organ Class (SOC), High-Level Group Term (HLGT), High-Level Term (HLT), Preferred Term (PT), and Lower-Level Term (LLT) will be attached to the clinical database.

Adverse event data will be listed by subject. Treatment-emergent AE (TEAE) and Serious TEAE will be summarized by system organ class and preferred term using the current version the Medical Dictionary for Regulatory Activities (MedDRA).

8.5.3. Laboratory Evaluations

Selected laboratory data (clinical chemistry and hematology) will be summarized using only observed data. Absolute values and change from predose at all scheduled time points will be summarized.

Laboratory abnormalities will be graded using GSI Grading Scale for Severity of Adverse Events and Laboratory Abnormalities ([Appendix 4](#)) for analysis purposes.

Incidence of treatment-emergent laboratory abnormalities, defined as values that increase at least one toxicity grade from predose at any time postdose up to the completion of study follow-up, will be summarized. If predose data are missing, then any graded abnormality (ie, at least a Grade 1) will be considered treatment emergent.

Laboratory abnormalities that occur before the first dose of investigational medicinal product or after the completion of study follow-up will be included in a data listing.

8.5.4. Other Safety Evaluations

ECG data will be summarized over time and presented in a listing.

Individual data for vital signs measurements will be listed by subject and summarized using incidence (frequencies) of events/ abnormalities or descriptive statistical summaries (eg, n, mean, SD, median, and range), as appropriate.

8.6. Pharmacokinetic Analysis

Plasma concentrations of ENTO and/or its metabolites (if applicable) over sampling time will be listed and summarized by hepatic function group and smoking status (Cohort 1 only).

Plasma concentrations of ENTO and/or its metabolites (if applicable) over time will be plotted in semi-logarithmic and linear formats as mean \pm SD and as median (Q1, Q3).

The PK parameters will be listed and summarized for ENTO and/or its metabolites (if applicable) using descriptive statistics (e.g., sample size, arithmetic mean, geometric mean, % CV, SD, median, minimum, and maximum) by hepatic function group (normal or CPT Class A, B, or C) and smoking status (Cohort 1 only).

A parametric (normal theory) ANOVA model appropriate for a parallel design will be fitted to the natural logarithmic transformation of PK parameters (AUC_{τ} and C_{\max}) for ENTO and/or its metabolites (if applicable). The 90% CIs will be constructed for the GLSM ratios of PK parameters for ENTO and/or its metabolites (if applicable) in each hepatic impairment group versus the matched control (normal hepatic function) group (and for Cohort 1, stratified by smoking status). The 90% CIs will be examined to determine if the GLSM ratio is within limits of 50% to 200%.

ENTO percent protein binding will be summarized by hepatic function group and smoking status (Cohort 1 only), and data for individual subjects will be presented in a listing (if applicable).

8.7. Sample Size

A sample size of 8 evaluable subjects per hepatic function group (for Cohort 1, it is 8 evaluable subjects per hepatic function group within each smoking status group) will provide

a \geq 89% probability for the 90% CI for the GLSM ratio of pharmacokinetic parameters (AUC or C_{\max}) for ENTO in the hepatic impairment/dysfunction group(s) versus the appropriate group of matched controls, to be within limits of 50% to 200%. The calculation assumes an expected ratio of geometric means of 1.0 in pharmacokinetic parameters and inter-subject standard deviation of 0.455 for the natural logarithm-transformed pharmacokinetic parameters for ENTO. The assumption is based on the data obtained from a prior clinical study of ENTO (Study GS-US-339-0111).

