In vitro studies indicate that ENTO is primarily metabolized by CYP2C9, and to a lesser extent by CYP3A and CYP1A2. Use of nicotine-containing or THC-containing products may induce CYP1A2, which has the potential to affect ENTO metabolism. Due to lower observed ENTO exposure in smokers in Cohort 1, enrollment in Cohort 1 has been expanded to enroll 10 smokers with moderate hepatic impairment (for 8 evaluable) and appropriate matched healthy controls, in order to further investigate the impact of smoking on ENTO PK. To avoid the potentially confounding effect of smoking on the assessment of hepatic impairment on ENTO PK, additional non-smoking subjects with moderate hepatic impairment will also be enrolled in Cohort 1 (10 enrolled for 8 evaluable, and appropriate healthy, matched controls). In Cohorts 2 and 3, only non-smoking subjects with hepatic impairment will be enrolled so that an accurate assessment of the effect of hepatic impairment on ENTO PK can be made, without the potentially confounding effect of smoking.

The trial will enroll subjects with chronically impaired hepatic function and healthy controls, matched for body mass index, age, and sex. This study will proceed in a staggered fashion. Dosing of subjects with mild and/or severe hepatic impairment will occur only after the review of safety and PK from smoking and non-smoking subjects with moderate hepatic impairment. Specifically, Cohort 2 will be initiated if supported by safety and PK findings from subjects in Cohort 1. Cohort 3 will be enrolled if a clinically meaningful change (≥ 2 -fold mean difference from matched healthy controls) in the exposures of ENTO and/or metabolite (if applicable) exposure is identified in non-smoking hepatic impairment subjects in Cohort 1.

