3. STUDY DESIGN

3.1. Study Design

This protocol describes an open-label, parallel-group, adaptive, multiple-dose, Phase 1 study evaluating the pharmacokinetics of ENTO and/or its metabolites (if applicable), in subjects with impaired hepatic function relative to matched, healthy controls.

This study will enroll a minimum of 40 and a maximum of 80 subjects using an adaptive study design that includes up to 3 enrolled cohorts of subjects with hepatic impairment as well as matched healthy controls. Eligible subjects will be male and nonpregnant, nonlactating female subjects, aged ≥ 18 years, $18 \leq \text{BMI} \leq 40$, with either impaired hepatic function of CPT classification A, B, or C or with normal hepatic function. Each subject in the control group will be matched to a subject with impaired hepatic function by age (± 10 years), gender, and body mass index ($\pm 20\%$).

When feasible, dosing in a matched control subject with normal hepatic function will occur after the subject with impaired hepatic function has completed the PK assessments, except if data exist from a subject with normal hepatic function in a previous cohort, this will be used instead of enrolling an additional normal healthy control subject, as permitted in adaptive Cohorts 2 and 3.

Cohort 1 enrollment of hepatic impairment subjects will be an approximate even distribution of subjects who are active cigarette smokers (at least 10 cigarettes/day) and subjects who are current non-smokers (no use of tobacco, nicotine-containing or THC-containing products within the last 14 days). Hepatic impairment subjects enrolled in adaptive Cohorts 2 and 3 will be current non-smokers (no use of tobacco, nicotine-containing or THC-containing products within the last 14 days).

Based on safety and/or PK results from the non-smoking subjects with moderate hepatic impairment and matching, healthy controls (Cohort 1), subjects with severe hepatic impairment (Cohort 2) and/or mild hepatic impairment (Cohort 3) will be enrolled as follows:

- Cohort 1 (CPT Class B, Moderate Hepatic Impairment)
Up to 40 subjects total:
20 with moderate impairment, (10 smokers [at least 8 evaluable] and 10 non-smokers [at least 8 evaluable]), 20 matched healthy controls (at least 8 evaluable healthy controls matched to smokers with moderate impairment, and at least 8 evaluable healthy controls matched to non-smokers with moderate impairment).
- Adaptive Cohort 2 (CPT Class C, Severe Hepatic Impairment)

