4.3.3. Healthy Matched Controlled Subjects

Healthy matched controlled subjects meeting *any* of the following additional exclusion criteria are not to be enrolled in this study:

- 1) Serious or active medical or psychiatric illness that, in the opinion of the Investigator, would interfere with subject treatment, assessment, or compliance with the protocol. This would include renal, cardiac, hematological, hepatic, pulmonary (including chronic asthma), endocrine (eg, diabetes), central nervous, gastrointestinal (including an ulcer), vascular, metabolic (thyroid disorders, adrenal disease), immunodeficiency disorders, active infection, or malignancy that are clinically significant or requiring treatment.
- 2) History of liver disease.

- 3) Have taken any prescription medications or over-the-counter medications, including herbal products, within 28 days prior to start of study drug dosing, with the exception of vitamins and/or acetaminophen and/or ibuprofen
- 4) Positive test for drugs of abuse, including alcohol at Screening or on Day -1/check-in
- 5) Subjects will be required to refrain from the use of nicotine, nicotine-containing products (including cigarette smoking) or THC-containing products for at least 14 days prior to first dose of study drug, and during the course of the study through the follow-up visit

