### 5.2.2. Statistical Comparative Analysis

To evaluate the PK effect of hepatic impairment on ENTO and/or its metabolites (if applicable), the PK parameters ( $AUC_{0-12}$  (day 1),  $AUC_{tau}$  (day 5), and  $C_{max}$  (day 1 and 5)), will be compared between impaired hepatic function group (test) vs normal hepatic function group (reference)

within each smoking status group (Cohort 1 only) after natural log transformation. The primary comparison will be based on day 5 PK parameters ( $AUC_{\tau}$  and  $C_{\max}$ ).

To evaluate the smoking effect on PK of ENTO and/or its metabolites (if applicable), the PK parameters ( $AUC_{0-12}$  (day 1),  $AUC_{\tau}$  (day 5), and  $C_{\max}$  (day 1 and 5)), will be compared between smoking group (test) vs nonsmoking group (reference) within Cohort 1 hepatic impaired subjects after natural log transformation. The primary comparison will be based on day 5 PK parameters ( $AUC_{\tau}$  and  $C_{\max}$ ).

A parametric (normal theory) ANOVA model will be fitted to the natural log-transformed PK parameter using SAS® PROC MIXED. The model will include hepatic function as a fixed effect. The 2-sided 90% CIs will be constructed for the ratio of geometric least-squares means (impaired hepatic function group /normal hepatic function group).

The following SAS® PROC MIXED code will be used in the comparison analysis described above and the 90% confidence intervals (CIs) will be constructed for the ratio of geometric least-squares means of PK parameters.

```
Proc Mixed method=reml;
*where smoking status eq "Yes"; Cohort 1 only
*where smoking status eq "No"; Cohort 1 only
*where hepatic impaired, Cohort 1 only
  class hepgrp;
  *class smoking status;
  model lnest = hepgrp / ddfm=kr;
  repeated / group = hepgrp;
  lsmeans hepgrp / e diff cl alpha = 0.1;
  estimate 'Impaired versus Normal' hepgrp 1 -1 / cl alpha = 0.10;
  *model lnest = smoking status / ddfm=kr;
  *repeated / group = smoking status;
  *lsmeans smoking_status / e diff cl alpha = 0.1;
  *estimate 'Smoking vs Nonsmoking HI subjects in Cohort 1' smoking_status 1 -1 / cl
alpha = 0.10;
  ods output Estimates = LS_Diffs LSMeans = LS_Means CovParms = MSE;
Run;
```

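### With 8 evaluable per group the chance of a 90% CI within 50%–200% is at most about 79%, not ≥89%, and for Cohort 1 smokers the assumed ratio of 1.0 is itself unsupported

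*Protocol*

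**What the plan says.** Protocol 8.7 bases the sample size on the probability that the 90% CI falls inside 50% to 200%, puts that probability at 89% or more, and applies it to every comparison. For the first cohort it says "for Cohort 1, it is 8 evaluable subjects per hepatic function group within each smoking status group". Two inputs are given: "The calculation assumes an expected ratio of geometric means of 1.0 in pharmacokinetic parameters", and an "inter-subject standard deviation of 0.455 for the natural logarithm-transformed pharmacokinetic parameters for ENTO". The synopsis and SAP 1.4 repeat the statement.

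The protocol's analysis criterion uses both limits (8.6): "The 90% CIs will be examined to determine if the GLSM ratio is within limits of 50% to 200" percent. The SAP builds the same interval (5.2.2): "The 2-sided 90% CIs will be constructed for the ratio of geometric least-squares means". Its decision rule, however, looks only at whether the upper bound is below 2.0.

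On smoking, Protocol 1.3 says: "Due to lower observed ENTO exposure in smokers in Cohort 1, enrollment in Cohort 1 has been expanded". Section 4.3.3 requires of healthy controls: "Subjects will be required to refrain from the use of nicotine, nicotine-containing products (including cigarette smoking) or THC-containing products for at least 14 days" before dosing, and also through follow-up. Section 5.6.2 exempts only the smoking subjects with hepatic impairment in Cohort 1. Matching is on age, gender and BMI (4.1); smoking is not a matching factor.

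**The concern.** There are two separate problems with one sentence.

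First, the sentence describes a two-limit event, but its number looks like a one-limit probability. If so, it overstates the chance of meeting the protocol's criterion in every cohort and stratum, with or without smokers.

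Second, the sentence gives the smoker stratum the same ratio of 1.0 as the others. In a matched hepatic impairment study, 1.0 is the no-hepatic-effect scenario. Here the numerator is impaired smokers and the denominator is non-smoking healthy subjects. Removing the hepatic effect therefore leaves the smoking effect, which the protocol reports as lowering exposure. Correcting only the first problem would leave the smoker figure resting on an input that the same protocol calls into question.

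What is at stake is the stated planning probability for a comparison under the primary objective. A reader who relies on it would expect a tighter result than the design delivers.

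**Working it through.** **Inputs.** 8 versus 8 evaluable, log SD 0.455 and true ratio 1.0 (Protocol 8.7); two-sided 90% CI (SAP 5.2.2); limits 0.5 and 2.0, which are ±0.693 on the log scale (Protocol 8.6). The analysis is a two-group parallel comparison with 14 degrees of freedom.

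**CI width.**
- Standard error = 0.455 × √(2/8) = 0.2275.
- Expected half-width = 1.761 × 0.2275 = 0.401, a factor of exp(0.401) = 1.49 each side of the ratio.

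**The stated figure at ratio 1.0.**
- The distance to either limit is 0.693/0.2275 = 3.05 standard errors. The noncentral t distribution (14 df) gives P(upper limit < 2.0) = 89.4%.
- By symmetry P(lower limit > 0.5) is also 89.4%.
- P(both) = 0.8943 + 0.8943 − 1 = 0.7886, or 78.9%. Integrating over the distribution of the variance gives the same value.

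The printed ≥89% therefore matches the upper limit alone. It does not match the two-limit event that the sentence describes. Other readings at ratio 1.0, both limits:

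| Reading | Probability |
|---|---|
| 8 vs 8, pooled variance | 78.9% |
| 8 vs 8, unequal variances (simulated) | 78.3% |
| 8 vs 8, error df pooled over 4 groups | 81.6% |
| 8 vs 8, 0.455 read as a CV | 83.6% |
| 8 vs 8, normal approximation | 83.9% |
| 9 vs 9 | 85.2% |
| 10 vs 10 | 89.7% |
| 8 vs 16 controls | 92.2% |
| 8 pairs, SD of the difference 0.455 | 97.3% |

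Only the last three reach 89%, and none is what the text states. It specifies 8 evaluable per group, an inter-subject SD and a parallel-design ANOVA.

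**The smoker stratum.** The true ratio is (hepatic effect) × (smoking effect). With no hepatic effect it equals the smoking effect. The documents give no size for that effect, so the ratios below are assumptions. The same formula is used: P(both) = P(upper < 2.0) + P(lower > 0.5) − 1. At 0.8, for example, 0.9853 + 0.6254 − 1 = 0.6107.

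| Assumed true ratio | Both limits, 8 vs 8 | Upper limit < 2.0 only, 8 vs 8 | Both limits, 10 vs 10 |
|---|---|---|---|
| 1.0 | 78.9% | 89.4% | 89.7% |
| 0.9 | 74.6% | 95.4% | 85.5% |
| 0.8 | 61.1% | 98.5% | 71.4% |
| 0.7 | 40.3% | 99.7% | 47.8% |
| 0.6 | 18.9% | >99.9% | 21.7% |

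At 8 versus 8 the two-limit probability crosses 50% at a ratio of about 0.74.

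**Offset.** A hepatic effect of 1.25 with a smoking effect of 0.8 gives 1.25 × 0.8 = 1.0, and the probability returns to 78.9%.

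**The case against.** The strongest reply is that the sizing statement is conditional: it says what happens at a ratio of 1.0 and does not claim that smokers will sit there. That is fair for the smoking part, which challenges an assumption and does not show a calculation error. It does not rescue the printed figure, because the two-limit value at exactly 1.0 is still 78.9%.

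A second reply is that under the SAP's upper-bound rule the figure is sound. This also stands. At 1.0 the probability is 89.4%, and any ratio below 1.0 raises it, so for that rule the statement is conservative in smokers. But the sentence names both limits, and so does Protocol 8.6.

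Third, no enrolment decision is clearly tied to the smoker comparison. Cohort 3 opens on the non-smoking impaired subjects. Protocol 3.1 and 5.3 base Cohort 2 on non-smokers too, although 1.3 refers to Cohort 1 subjects generally. This limits the consequence to the planning statement.

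A reader might infer two stronger points that the documents do not support:

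- **That the smoker comparison will probably miss the 50%–200% criterion.** That needs a true ratio below about 0.74. Protocol 1.3 gives neither the size of the smoking difference nor its comparator, and it describes CYP1A2 as a lesser pathway than CYP2C9. Protocol 1.3.1 allows for exposure to rise with impairment, which would work the other way.
- **That the ≥89% is sound outside the smoker stratum.** As worded, it fails there too.

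**Conclusion.** The stated probability is wrong as written. For 8 versus 8 evaluable, log SD 0.455 and a parallel two-group analysis, the chance that both 90% limits fall within 50%–200% is at most 78.9%, about 10 points below the stated minimum. This applies to every cohort and stratum sized this way.

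In the Cohort 1 smoker stratum the ratio of 1.0 additionally lacks support. At assumed ratios of 0.9, 0.8 and 0.7 the two-limit probability falls a further 4, 18 and 39 points below 78.9%. How much of that loss applies cannot be derived from the documents. It depends on an unreported smoking effect and on any offsetting hepatic effect. With a common hepatic effect in both strata, the ratio can be 1.0 in both only if smoking has no effect.

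**What to change.** Amend Protocol 8.7, the synopsis and SAP 1.4 together.

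1. For the non-smoker stratum of Cohort 1 and for Cohorts 2 and 3, restate the figure at ratio 1.0 as about 79% for both limits within 50%–200%. Alternatively, give about 89% for the upper limit below 2.0 and name that as the criterion.
2. For the smoker stratum, tabulate the probability over true ratios of 0.6 to 1.0, stating that the comparison is against non-smoking controls. Alternatively, drop the probability there and give the expected 90% CI width, a factor of about 1.49 each side.

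Leave the number of subjects unchanged. The cost is wording in three places and one short calculation. The downside is a less favourable stated figure.
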